This work aims to advance Brain-Computer-Interfaces (BCIs) to provide severely paralyzed persons a natural way of controlling Functional Electrical Stimulation (FES) neuroprostheses for restoring arm and dexterous hand movements. The prospect of using BCI technology for restoring arm and hand movements for reaching and grasping is based on the hypothesis that in a paralyzed human, there is a repeatable and understandable relationship between recordable brain activity and specific aspects of imagined arm movements. Many previous studies have attempted to understand the relationships between brain activity and arm and hand movements in able-bodied monkeys. Little is known about these same relationships in humans, and specifically within the context of trying to control an FES arm and complex hand system. This study will recruit persons who already have BCI and FES systems implanted to take advantage of the possibility of recording high resolution brain activity in human participants. Thus, from this study, we aim to gain a better understanding of how brain signals are related to specific aspects of arm and complex hand movements in humans with paralysis. Additionally, this study will test novel implementations of complex hand movement restoration in Veterans and other persons with chronic hand and arm paralysis.

10. Describe the means of analyzing the data and evaluating the results.

- *State the anticipated methods to be used for analysis and interpretation of the data.*
- *The methods must compliment the design of the study and the nature of the data which is being collected.*

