From the recorded brain activity, the data analysis will consist of developing mathematical models which attempt to correlate the brain activity to movement parameters of the hand (e.g. finger angles, and whole hand states). We will investigate several different correlation models, which focus on extracting information from different aspects (i.e. features and/or frequencies) of the neural activity. We will use correlation models based upon linear regression, neural networks, and system identification. We will test these models under a variety of scenarios, including varying levels of signal variation and noise. The analysis will result in correlation models that will be assessed by how well they are able to predict the hand states and continuous arm and finger movements required for grasping function. The metric of efficacy will be the Variance Accounted For (%VAF), which is qualitatively similar to an r-squared metric. Effectively the correlation models are determining statistical (linear or nonlinear) fits of the neural data (input) to the desired hand movements (outputs). The returned p-values of these fits will assess if the models produce statistically significant correct predictions. The final result of these analyses will be one or more models that study participants will then use in a real-time application, using direct cortical signals, to control hand states and and arm and finger movements of their own FES arm and hand.

11. Provide a BRIEF DESCRIPTION of how the estimated number of study subjects needed for this research was determined

- *If this is a quantitative study provide the method of determining sample size estimates.*
- *If multiple studies are planned provide a power analysis or justification for each one.*

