This nature of this study is exploratory in nature (rather than quantitative) in that we aim to better understand how hand function is encoded in cortical signals, and then use this understanding to develop correlation models for real-time control of an FES neuroprosthesis. We need to tweak several parameters of each model based upon experimental data, and then test the optimized models in actual control experiments. Consequently the number of required subjects is not elucidated by a standard statistical power analysis. The present study does aim to enroll up to four persons with paralysis (C1-C4 SCI, resulting in complete tetraplegia) who already have intracortical brain arrays and FES systems implanted. The study leverages the clinical and recruiting efforts of the separately funded Braingate2 Clinical Trial in Cleveland that recruits persons with C1-C4 SCI to receive BCI and FES systems.

12. The research involves the following procedures conducted by and for what purpose:

PROCEDURE	PERFORMED BY:		PROCEDURE IS:	
	Research Staff	LSCDVAMC Clinical or Support Staff	Standard of Care*	For Research Purposes Only**
Audiotaping / Videotaping Attach VA Form 10-3203 REQUIRED ONLY FOR IN-PATIENT AND OUT-PATIENT SUBJECTS				
Biopsy				
Blood collection				
Chart review – prospective				
Chart review – retrospective				
Review of existing data (ex: registry, Database , etc.)				
X-ray or Ionizing radiation exposure				
Clinical Tests				
Device implantation				
Drug administration				

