EEG, EKG , ECG...etc				
Gene therapy, Genetic analysis				
Pregnancy/Breastfeeding Screening				

PROCEDURE	PERFORMED BY:		PROCEDURE IS:	
	Research Staff	LSCDVAMC Clinical or Support Staff	Standard of Care*	For Research Purposes Only**
Interview, Questionnaire, Diary, Survey (please attach)				
Stool collection, Urine collection, or any Non-surgical Specimen collection				
Surgical procedure or Specimen removal during surgery				
Tissue banking (complete Section 12)				
Use of pre-existing tissues/specimens				
Other (list) : EMG				

- **Standard of care procedures are procedures performed in the course of normal medical care.*
- ***Research Procedures are performed for the purposes of this research alone.*

13. Please describe the research design and all study related procedures.

- *Describe **ALL PROCEDURES ASSOCIATED WITH THIS RESEARCH**. This includes standard of care and research procedures.*
- *For complex studies please include diagrams and tables. Be sure to describe when each procedure will be performed. Be sure to provide information for **each cohort, including normal controls**.*

All study participants will have already had implanted one or two 96-channel microelectrode arrays in the primary motor cortex (M1), as well as stimulating electrodes for restoration of hand and arm function via FES.

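### For continuous movements analysed in time bins, the p-values returned by the model fits do not show that predictions are correct; replace them with a held-out score and a null that keeps serial dependence

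*Combined protocol and SAP*

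**What the plan says.** All references are to the combined protocol and SAP.

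- Section 3, item 9 states the working hypothesis: "there is a repeatable and understandable relationship between recordable brain activity and specific aspects of imagined arm movements".
- Section 3, item 10 names the model classes: "We will use correlation models based upon linear regression, neural networks, and system identification". The outputs are hand states and "continuous arm and finger movements required for grasping function".
- Item 10 sets the performance measure: "The metric of efficacy will be the Variance Accounted For (%VAF), which is qualitatively similar to an r-squared metric". It does not say whether this is computed on the fitted data or on new data.
- Item 10 adds a robustness step: "We will test these models under a variety of scenarios, including varying levels of signal variation and noise".
- Item 10 then gives the significance rule: "The returned p-values of these fits will assess if the models produce statistically significant correct predictions". It names no test statistic, reference distribution or alpha.
- Section 3, item 11 calls the study exploratory and says: "We need to tweak several parameters of each model based upon experimental data, and then test the optimized models in actual control experiments".
- Section 3, item 13 gives one or two 96-channel arrays per participant and sampling at 30 kHz. It describes offline discrimination of movement patterns by LDA and SVM, followed by closed-loop trials with the best algorithm. It does not describe cue order.

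No section mentions held-out data, cross-validation, permutation, a correction for serial dependence or a bin width.

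**The concern.** A fit p-value has a meaning only under the conditions of its test. Three of them are doubtful for movement recorded as a time series.

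- **Target of the test.** The p-value of a fit says whether inputs and outputs are associated in the data used for fitting. It does not say whether the model predicts new data.
- **Independence.** Arm and finger positions change smoothly, so neighbouring bins carry much the same information. If the neural features are also serially correlated, the nominal number of observations overstates the real information.
- **A model fixed in advance.** Item 11 says that parameters are tuned on experimental data, which the returned p-value does not reflect.

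At stake is what gets reported as encoded. This p-value is the only significance test that the plan attaches to the offline predictions, and item 9 asks about specific aspects of movement. A statement that a given finger angle is significantly predicted could be false far more often than the nominal level suggests.

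**Working it through.** The plan states no error rate, so there is no figure to reproduce. The check asks how often a fit p-value falls below 0.05 when the movement is unrelated to the neural data.

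**Inputs from the plan.** 96 or 192 channels (1 or 2 × 96, item 13), continuous outputs, and linear regression as one of the named classes (item 10).

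**Assumptions, none in the plan.** Alpha 0.05; one feature per channel; 50 ms bins over 5 minutes (300 s / 0.05 s = 6,000 bins); independent AR(1) channels with lag-1 autocorrelation a; movement with lag-1 autocorrelation b, or a target-to-target path (2 s move, 1 s hold).

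**Step 1: large-sample formula for the overall F-test.** Serial dependence in both series inflates the regression sum of squares by v = (1 + ab)/(1 − ab). With p features, the null rejection rate is about P(χ²_p > c/v), where c is the 95th percentile of χ²_p: 119.87 for p = 96 and 225.33 for p = 192. For example, a = 0.1 and b = 0.9 give v = 1.09/0.91 = 1.198 and c/v = 100.08 for p = 96, hence 36.8%.

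| a | b | v | 96 channels | 192 channels |
|---|---|---|---|---|
| 0 | any | 1 | 5% | 5% |
| 0.1 | 0.5 | 1.105 | 18.1% | 26.5% |
| 0.1 | 0.9 | 1.198 | 36.8% | 56.6% |
| 0.1 | 0.99 | 1.220 | 41.6% | 63.4% |
| 0.6 | 0.5 | 1.857 | 99.4% | 100% |
| 0.6 | 0.9 | 3.348 | 100% | 100% |

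Fewer features inflate less. At a = 0.1, b = 0.99 the formula gives 7.6% for 1 feature, 13% for 10 and 21% for 30.

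**Step 2: simulation of the F-test** (6,000 bins; 300 null data sets per cell for 96 channels, 200 for 192).

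| Movement | Channels | a = 0 | a = 0.1 | a = 0.6 |
|---|---|---|---|---|
| Target-to-target | 96 | 6.0% | 39.3% | 100% |
| Target-to-target | 192 | 5.5% | 62.5% | 100% |
| AR(1), b = 0.9 | 96 | 7.3% | 36.0% | 100% |
| AR(1), b = 0.9 | 192 | 4.0% | 55.0% | 100% |
| AR(1), b = 0.5 | 96 | 5.3% | 20.0% | 100% |
| AR(1), b = 0.5 | 192 | 4.5% | 26.5% | 100% |

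Smaller repeat runs (60 to 150 data sets per cell) reached down to about 15% at a = 0.1 with b = 0.5, and to 98% at a = 0.6. The fair ranges are therefore about 15-63% and 98-100%. With 30 minutes of target-to-target data the rates at a = 0.1 were 49% (96 channels) and 63% (192), so more recording does not cure the problem.

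**Step 3: the other reading.** Train on the first 80% of the data, then take the ordinary p-value of the correlation between predicted and actual bins in the rest. Null rejection was 4-6% at a = 0, 4-8% at a = 0.1 and 15-35% at a = 0.6. Repeat runs gave about 2-10% and 12-38% for the last two. Separate data remove most of the inflation at low autocorrelation, but not at 0.6.

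**Step 4: what held-out %VAF shows.** Mean held-out VAF was negative in every null setting. For target-to-target movement and 96 channels it was −10% at a = 0.1 and −17% at a = 0.6. The held-out score shows a failure that the fit p-value hides.

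**Step 5: boundary.** With one row per trial (600 trials) null rejection was 1.7-6.3%. Classification once per trial is therefore not affected.

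**The case against.** - **The test is unnamed, so the size is unknown.** This stands. A reader might infer that this trial's false-positive rate will be 15-63%, or near 100%. The documents do not support that: test, bin width, duration, alpha, feature count and autocorrelations are all absent. Item 10 also speaks of assessing how well models predict, which leaves room for the milder reading in step 3. The principle does not depend on these rates, because neither reading allows for serial dependence.
- **Models are later run on new trials.** Items 11 and 13 do test optimised models in closed-loop and control experiments. A reader might infer that the plan never evaluates its models on new data, and that would be wrong. Those steps would probably expose a useless decoder, but they carry no significance test and do not replace the item 10 rule.
- **Item 13 describes LDA and SVM.** Correct. A reader might extend the point to the whole offline analysis, but discrimination once per trial lies outside it.
- **Participants already show neural control.** Section 4, item 30 requires cursor control, so some signal exists. That does not settle whether a particular finger angle is encoded. In a simulation of 100 out-and-back trials, 96 channels encoded the arm but not an independently cued finger. The finger F-test rejected in 21-47% of data sets with uncorrelated channel noise and in 57-79% at noise lag-1 0.1. The held-out correlation rejected in 15-50%.
- **The study is exploratory.** That explains the absence of a power calculation. It does not make a stated test valid, though it does limit the consequences.

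**Conclusion.** The point holds for continuous movements analysed in time bins. As written, the rule treats an in-sample association p-value, computed as if bins were independent and the model fixed in advance, as evidence of correct prediction. No other section corrects it. This is a wrong rule rather than missing detail.

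The size is conditional on the assumptions listed above. Under the F-test reading, null rejection is about 15-63% at channel lag-1 0.1 and 98-100% at 0.6. Under the held-out-correlation reading it is near nominal to about 10%, and about 12-38%. It is about 5% if the channels are serially uncorrelated, and inflation shrinks with fewer features.

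The harm is confined to reported claims that a given movement parameter is encoded. A reader might infer that decoder choice, closed-loop testing or participant safety is compromised. The documents do not support this: %VAF, not the p-value, is the efficacy metric, and nothing in enrolment or safety monitoring uses the p-value. The sentence should be corrected, but it does not undermine the study.

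**What to change.** Replace the p-value sentence in Section 3, item 10 with:

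> Models are fitted and tuned on training blocks only. %VAF (or classification accuracy) is reported on whole held-out blocks or sessions. For each movement parameter within participant, significance is judged by comparing the held-out score with its distribution when whole-trial labels of the held-out trials are permuted with the fitted model unchanged. Where cue order is not randomised or movement is not trial-based, another null that preserves serial dependence, such as circular shifts, is used. Held-out %VAF is reported beside every p-value, and a result with %VAF at or below zero is described as association, not as correct prediction. Fit p-values are not used as evidence of correct prediction.

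Because the model is not refitted, the same rule serves linear regression, neural networks and system identification.

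**Error control.** In simulated out-and-back trials in random order, the permutation test rejected in 116 of 2,400 global-null data sets (4.8%) and 109 of 2,000 with only the arm encoded (5.5%). Circular shifts were checked only on the in-sample F statistic (1,200 bins) and gave 3.3-6.3%.

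**Cost.** A little more analysis code and one paragraph, with no new data. Reported VAF will be lower and slightly noisier, and some weak encoding will be missed or labelled association only. With 96 channels at lag-1 0.9 and 100 trials, the permutation test is significant in 84% of data sets when held-out VAF averages −7%, 97% at 5% and 99% at 24%. The share also reaching positive VAF, and so described as correct prediction, is 36%, 65% and 93%. The rule works per parameter and does not adjust for the number of parameters tested.

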Spinal cord injury (SCI) resulting in paralysis affects over 250,000 people nationwide with over 12,000 new cases each year. Slightly more than half of all SCI cases occur at cervical levels (tetraplegia). Incomplete and complete tetraplegia have accounted respectively for 34% and 18% of all SCI cases since 2000, with less than 1% of all cases achieving full recovery [1]. Veterans comprise almost 20% of SCI patients [2]. Even with a caregiver, many of these individuals experience a lower quality of life due to loss of personal independence from the inability to perform standard activities-of-daily-living (ADL) on their own, such as grasping objects for drinking and self-feeding.

Veterans and others with low cervical SCI (C5-C7) resulting in chronic hand paralysis can regain grasp function through electromyogram (EMG i.e. muscle) commanded functional electrical stimulation (FES) neuroprostheses. However, Veterans and others with high cervical SCI (C1-C4) resulting in chronic tetraplegia have limited to no voluntary EMG function post-injury to use as a command source, and hence cannot adequately use current FES grasp prostheses. FES grasp prostheses restore the ability to cycle between two hand grasps, whereas able-bodied persons use at least six different hand grasps [3-5], in addition to individuated finger movements, when interacting with everyday objects. This discrepancy implies that even for Veterans who have the option of using current FES grasp prostheses, there are many tasks involving the hand that they could not do easily, or possibly at all. For FES grasp prostheses to approach the dexterity of able-bodied grasping, and to be relevant to persons with C1-C4 SCI, fundamental advances are needed in 1) how grasp function is implemented, and 2) the command source used. The present study thus aims to investigate novel methods and interfaces for providing highly dexterous hand and arm function to Veterans and others primarily with high cervical SCI, with applicability to Veterans and others with low cervical SCI and other injuries resulting in hand and arm movement impairment.

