command the three dimensional movements of a robotic arm to pick up and drink from a cup [6], as well as perform dexterous robotic hand manipulations [7-8]. Recently, investigators have demonstrated that a human implanted with an iBCI could command up to ten dimensions of a robotic arm and hand, to pick up and transport selected objects [9]. Recently, investigators at Case Western Reserve University have demonstrated a person with chronic paralysis commanding the single-joint movements of his own paralyzed arm and hand, powered by FES, using an iBCI [10]. The participant used this FES+iBCI system to grasp and drink from a cup of coffee, and hold a fork and feed himself from a bowl of mashed potatoes. The present study aims to advance the clinical viability and dexterity of these system using two implementation methods for dexterous hand grasping and continuous arm movements An iBCI will be used as the command source to expand grasp functionality and arm movements and ultimately independence in persons with chronic and severe paralysis. iBCIs may offer to persons with C1-C4 SCI a viable means of commanding the high dimensional hand and arm functions required for increased reaching and grasp functionality. Persons with paralysis are highly amenable to receiving iBCIs, provided that the functional gain is significant over less invasive command sources [11-13]. Success of the present proposal will thus establish novel methods for restoring high-dimensional hand grasp and arm reaching function for Veterans and others with chronic paralysis, and quantitatively compare an FES+iBCI hand neuroprosthesis with currently available FES+EMG grasp prostheses in functional assessment tasks.

REFERENCES

- [1] NSCISC. Spinal cord injury. Facts and figures at a glance. *J. Spinal Cord Med.* 36, 1–2 (2013).
- [2] VA. VA and Spinal Cord Injury: Fact Sheet. (2007).
- [4] Ajiboye, A. B. & Weir, R. F. Fuzzy C-means clustering analysis of the EMG patterns of six major hand grasps. *Proc. 2005 IEEE 9th Int. Conf. Rehabil. Robot.* 2005, 49–52 (2005).
- [5] Birdwell, J. A., Hargrove, L. J., Weir, R. F. & Kuiken, T. A. Extrinsic finger and thumb muscles command a virtual hand to allow individual finger and grasp control. *IEEE Trans. Biomed. Eng.* 62, 218–226 (2015).

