Study participants will be instructed to imagine and attempt to perform various virtual finger, hand, and arm movements on a computer screen. Participants will be seated in front of a 3D monitor and observe a virtual arm/hand perform the movements. If needed to help perceive the 3D animation, the participant may wear stereoscopic glasses. Neural activity, sampled at 30 kHz, will be recorded during this motor imagery exercise. Offline, we will use standard discriminant algorithms, including linear discriminant analysis (LDA), and support vector machines (SVM), to investigate how well separated the movement patterns are based upon the neural activity alone. Participants will then use the best of these algorithms to perform a virtual "closed-loop" task. Similar to the above study, participants will be instructed to imagine and attempt to perform various hand and arm movements as presented on the computer screen. As the user imagines these movements, the recorded brain activity will be converted in real-time, through the algorithm, into movements of the virtual arm and hand. When the brain-controlled movements match the instructed movements, the participant will receive a cue indicating success. The participants will perform several trials of this task to assess how well they can perform this brain control of hand and arm movements and how well the algorithms decode their intended movements.

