Participants will also attempt to command movements of their paralyzed limb reanimated through functional electrical stimulation (FES). They will first do so using the iBCI and optimized algorithm that converts brain activity into a desired movement command. The desired movement command will be converted into electrical stimulation patterns that will be applied to the paralyzed muscles. A low frequency electrical stimulus will be sent to each appropriate muscle to cause it to contract and move as the participant has mentally instructed. The participants will attempt to use his brain-controlled paralyzed arm to perform a series of standard clinical tasks where they are required to pick up and move objects from point A to point B. Participants will also attempt to perform these same clinical tasks using standard electromyography (EMG) signals to command the paralyzed arm and hand, to compare to the performance of the brain control. Surface electrodes for recording muscle activity will be placed on muscles still under voluntary control, such as the platysma (neck) and aricularis (ear) muscles. When participants contract these muscles, EMG signals will be differentially recorded, filtered (10-1000 Hz), amplified, sampled, and smoothed at 20 Hz to produce the EMG envelope as a command signal. This command signal will then control the stimulation of the desired paralyzed muscles, and hence the movements of the paralyzed but reanimated arm and hand. This implementation is comparable to current EMG controlled FES systems, and performance using this approach will be compared to performance using the brain interface approach.

14. Will the research involve the following?

N/A Chart/Data Review

Placebo Group No Yes (describe):

Other Control Group No Yes (describe):

Randomization No Yes (describe):

Deception No Yes (describe):

15. Does the research involve the use and/or disclosure of Individually Identifiable Health Information in any form or medium?

No Yes If yes, complete the required HIPAA Waiver/Authorization forms.

16. Does the study include the administration of a study agent that does not require FDA approval and does not require an IND (e.g. vitamins, food supplements, isotope tracers, alternative medicines, etc.)?

No Yes -provide a detailed description of the procedures used to assure patient safety:

17. Will radioactive material be administered or will subjects be exposed to ionizing radiation?

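### The iBCI-versus-EMG comparison has no balanced test order, and on the natural reading iBCI is tested first

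*Combined protocol and SAP*

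**What the plan says.** Item 8 (background) gives as one outcome of the project that it will "quantitatively compare an FES+iBCI hand neuroprosthesis with currently available FES+EMG grasp prostheses in functional assessment tasks". Item 13 (research design and procedures) describes how. Participants command the FES-driven limb: "They will first do so using the iBCI and optimized algorithm that converts brain activity into a desired movement command". They use the brain-controlled arm for a set of clinical object-moving tasks. Then comes the comparator: "Participants will also attempt to perform these same clinical tasks using standard electromyography (EMG) signals to command the paralyzed arm and hand, to compare". The item closes by repeating that the two approaches will be compared.

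The word *first* is the only indication of order between the two command sources. No section describes counterbalancing, alternation or a randomised order. The randomisation line of item 14 reads "Randomization No Yes (describe" with no description after it. The tick itself is not legible in the text available, so nothing is inferred from it. The form's own instruction for item 13 is "Be sure to describe when each procedure will be performed".

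On prior exposure, item 30 requires that entrants have already shown neural cursor control. Item 13 describes a virtual closed-loop task before the FES tasks: "The participants will perform several trials of this task to assess how well they can perform this brain control of hand and arm movements". For EMG, item 13 describes electrode placement and signal processing, but no practice.

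**The concern.** Each participant is to perform the same tasks under two command sources, and the difference is to be reported. Performance on repeated object tasks can change for reasons unrelated to the command source, such as learning the tasks, fatigue within a session, or drift over sessions. If one source is always tested before the other, those changes are mixed into the difference. A difference in either direction, or the absence of one, could then partly reflect order.

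The study is small (item 20: 4 participants in Cleveland; item 21: 6 in all), so the within-participant contrast carries the comparison. Recruiting more people in the same fixed order would not help.

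**Working it through.** The document gives no figure for an order effect and no power calculation for this comparison, so there is nothing to reproduce. The check is structural.

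**Model (assumed).** Let *d* be the true iBCI-minus-EMG difference. Let *o* be the mean change in score from being tested second, taken as equal for both modes and constant over comparison units. A unit is one paired iBCI and EMG assessment in one participant.

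- iBCI first: observed difference = d − o
- EMG first: observed difference = d + o
- iBCI first in a share *f* of the units: unadjusted mean = d − (2f − 1)o

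**Share of *o* left in the unadjusted mean**, |n(iBCI first) − n(EMG first)| / n:

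- 4:0 → 4/4 = 1.00
- 6:0 → 6/6 = 1.00
- 3:1 → 2/4 = 0.50
- 2:1 → 1/3 = 0.33
- 2:2 or 3:3 → 0

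So with iBCI always first the whole order effect remains, and going from 4 to 6 leaves it unchanged. A positive *o* (task learning) would favour EMG; a negative *o* (fatigue) would favour iBCI. The document does not say which applies.

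**With adjustment for order.** Once both orders have been observed, average the two order-specific means: [(d − o) + (d + o)]/2 = d, for any split. Imbalance then costs precision only. With n₁ and n₂ units in the two orders and equal unit variance, the variance relative to an equal split is n²/(4n₁n₂):

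- 3:1 → 16/12 = 1.33
- 2:1 → 9/8 = 1.13
- 3:2 → 25/24 = 1.04

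With only one order observed, n₁ or n₂ is zero and no adjusted estimate exists.

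**Illustration of the consequence (assumed values; the plan specifies no such test).** Take six participants, one comparison each, no true difference between modes, and a chance *q* that the second-tested mode scores better. A two-sided sign test requiring all six in one direction has nominal level 2 × 0.5⁶ = 0.031. With iBCI always first, the chance of a false finding is q⁶ + (1 − q)⁶. With three participants in each order, it is 2q³(1 − q)³.

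| q | iBCI always first | 3:3 |
|---|---|---|
| 0.5 | 0.031 | 0.031 |
| 0.6 | 0.051 | 0.028 |
| 0.7 | 0.118 | 0.019 |
| 0.8 | 0.262 | 0.008 |
| 0.9 | 0.531 | 0.001 |

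The value of *q* is unknown. The table shows only how a fixed order can pass for a difference between devices.

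**The case against.** The strongest reply is textual. In item 13 the word *first* attaches to commanding the FES limb, not to the clinical tasks, which follow without an order word, and EMG is introduced only as an addition. A reader might infer that the protocol certainly fixes iBCI before EMG on the compared tasks. The text does not go that far: it is the natural reading, not a certain one. This changes the description but does not remove the gap, because if *first* is narrative there is no order rule at all.

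A reader might also infer that no later analysis could separate order from command source. That holds only if iBCI precedes EMG in every unit. Item 22 allows up to 30 sessions per participant, and nothing says iBCI testing ends once EMG testing begins. If both orders happened to occur, adjustment would be possible, but the plan does not ensure it.

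On practice, a reader might infer that EMG will be used untrained and that the comparison therefore favours iBCI. The document is silent on EMG practice; it does not exclude it, and the sessions leave room for it. Item 8 does say that people with C1–C4 injury "have limited to no voluntary EMG function post-injury to use as a command source, and hence cannot adequately use current FES grasp prostheses", so prior EMG skill cannot be presumed in the group named in item 11. However, item 13 uses muscles that remain under voluntary control, and item 30 admits anyone with at least partial arm paralysis. Equal extra practice would not close the earlier iBCI exposure either. This part is therefore secondary.

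Finally, item 11 calls the study "exploratory in nature (rather than quantitative", item 10 names variance accounted for as the efficacy metric, and the purpose statement in item 9 does not mention EMG. These points lower the stakes. They do not withdraw the comparison promised in items 8 and 13.

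**Conclusion.** The point holds in limited form. The plan promises a quantitative within-participant comparison of iBCI and EMG command and does not balance the order of testing. If iBCI always comes first, the comparison contains the full order effect, of unknown size and direction. If the order is left open, it is uncontrolled. This rests on an additive order effect common to both modes.

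Because the study is exploratory, the consequence is a limit on interpretation, not the failure of a confirmatory test. Nor does the argument show that an even number of units per participant is required: in the model above, an order-adjusted estimate is unbiased for any split containing both orders, and an even number only helps precision. The matter is worth correcting before comparison testing starts, since data from a single order cannot be repaired afterwards.

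**What to change.** In item 13, keep decoder development first. For the comparison on the clinical tasks, add wording such as:

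> The order of iBCI and EMG command is balanced within each participant (alternated or randomised in pairs across comparison sessions), with the same objects and number of attempts for each mode, and the order is recorded.

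Alternation should mean that the starting mode switches from one pair to the next. State in advance whether a pair is tested within one session or over two adjacent sessions. Analyse the paired differences within participant with adjustment for order, and do not treat single trials as independent.

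As a secondary change, provide a short EMG practice period on the tasks before comparison testing and record prior exposure to each command source. Interpret the result as a comparison of the systems as set up, because the iBCI exposure built into items 13 and 30 cannot be matched.

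The cost in text is a few sentences and an order list per participant. In conduct there will be some extra EMG electrode placements (item 38 rates the skin irritation as occasional and mild) and some practice time. Testing both modes in one session means switching the setup within about 4 hours (item 22), with possible fatigue; using adjacent sessions adds day-to-day variation to each difference. Balancing also assumes no differential carry-over between modes. The document does not say how many of the up to 30 sessions are meant for this comparison, so the cost in sessions cannot be stated.
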